12.0 Potential Benefits to Participants and Others

12.1 Potential Benefits to Participants

Describe the potential benefits that individual participants may experience from taking part in the research. If there is no direct benefit to participants, indicate as such. Compensation is not considered a benefit. Compensation should be addressed in section 14.0.

Participants may experience some benefits from participation, this includes learning to better understand their mental health concerns, learning more about coping, reducing isolation from others, and reaching other individual goals set through with their research therapist.

Participants may also experience some occupational success as they learn to better manage their job interview phobia and access the skills they have to succeed in job interviews. The treatment is aimed to target reducing job interview phobia, one of the potential obstacles to occupational attainment and advancement.

Social anxiety has been linked to difficulties at work or in school and in social or romantic relationships. Therefore, a benefit of treating social interaction anxiety may be an increase in quality of life as individuals can more comfortably engage in daily situations in their personal and professional lives. A second benefit may be an increase in self-esteem. Social anxiety is also highly comorbid with depression. Therefore, treating the underlying source of distress that is rooted in social phobia may also yield additional gains when addressing multiple diagnoses.

12.2 Potential Benefits to Others

Include benefits to society or others.

The field of psychology lags behind many other disciplines with regard to incorporating technology into practice. This study will help to move the field forward by examining how technology can be incorporated to supplement existing treatments. It is the plan of the researchers to use the results of this study to help establish best practices for including technology into therapy and to identify more specific research questions for future study.

13.0 Sharing Results with Participants

Describe whether results (study results or individual participant results, such as results of investigational diagnostic tests, genetic tests, or incidental findings) will be shared with participants or others (e.g., the participant's primary care physicians) and if so, describe how it will be shared.

Not Applicable.

14.0 Subject Stipend (Compensation) and/or Travel Reimbursements

Describe the amount and timing of any subject stipend/payment or travel reimbursement here. If there is no subject stipend/payment or travel reimbursement, indicate as not applicable.

If course credit or extra credit is offered to participants, describe the amount of credit and the available alternatives. Alternatives should be equal in time and effort to the amount of course or extra credit offered.

If an existing, approved student subject pool will be used to enroll participants, please indicate as such and indicate that course credit will be given and alternatives will be offered as per the approved subject pool procedures.

The following compensation mechanism will be used for all participants: Participants will be awarded a \$40 gift card which will be reimbursed online via email within a week after they have completed the measures at 6-month follow-up. The planned payment is appropriate and mutually beneficial. It maximizes the chances that participants will engage fully with treatment to benefit themselves and complete all of the study procedures. Participants are expected to spend about 10 hours to complete the assessment batteries and therapy sessions. The money is reasonable in compensating their time. However, given that they are also receiving free treatment, we do not compensate them for time spent in therapy or homework from therapy. Further, this amount is not expected to cause undue coercion on the prospective research participants to partake in the study.

15.0 Economic Burden to Participants

15.1 Costs

Describe any costs that participants may be responsible for because of participation in the research.

There are no economic costs for participants in this study. Participant "costs" merely includes their time of investment and thought.

15.2 Compensation for research-related injury

If the research involves more than Minimal Risk to participants, describe the available compensation in the event of research related injury.

If there is no sponsor agreement that addresses compensation for medical care for research participants with a research-related injury, include the following text as written - DO NOT ALTER OR DELETE:

It is the policy of the institution to provide neither financial compensation nor free medical treatment for research-related injury. In the event of injury resulting from this research, medical treatment is available but will be provided at the usual charge. Costs for the treatment of research-related injuries will be charged to participants or their insurance carriers.

For sponsored research studies with a research agreement with the sponsor that addresses compensation for medical care for research-related injuries, include the following text as written - DO NOT ALTER OR DELETE:

It is the policy of the institution to provide neither financial compensation nor free medical treatment for research-related injury. In the event of injury resulting from this research, medical treatment is available but will be provided at the usual charge. Such charges may be paid by the study sponsor as outlined in the research agreement and explained in the consent form.

Not applicable.

16.0 Resources Available

16.1 Facilities and locations

Identify and describe the facilities, sites and locations where recruitment and study procedures will be performed.

If research will be conducted outside the United States, describe site-specific regulations or customs affecting the research, and describe the process for obtaining local ethical review. Also, describe the principal investigator's experience conducting research at these locations and familiarity with local culture.

Study participation and recruitment will occur in [name] research lab [348B, 348C, 381, 380, 348A and 378 Moore Building] as well as the therapy rooms in the Psych Clinic [301-325 Moore Building] on Penn State University Park campus.

The [name] Laboratory for Anxiety and Depression Research as well as PSU Psychological Clinic therapy rooms, located in the Moore Building, includes seating, desk space, and computers where participants will undergo the consenting process and experiment. Some research personnel will also be seated in the room to guide participants through the study.

16.2 Feasibility of recruiting the required number of participants

Indicate the number of potential participants to which the study team has access. Indicate the percentage of those potential participants needed for recruitment.

During each semester, approximately 800 students are enrolled in the subject pool who are expected to accumulate up to 6 hours of research credits as a course requirement. We would thus have access to a large numbers of people who are willing and able to partake in the present study. The PSU Psychology Subject Pool is thus an abundant resource for the recruitment of study participants and many previous studies with larger social anxiety disorder samples have been conducted within this participant pool. It is feasible that the desired/required number of participants can be recruited based on previous experience with the subject pool. For the past two semesters of subject pool research over 200 students have met criteria for social anxiety disorder via the Social Phobia Diagnostic Questionnaire.

Further, the Penn State Psychological Clinic is the best place for conducting this study primarily because the data is relatively unique to the clinic. The clinic is a rural outpatient community mental health clinic and will provide information generalizable to an understudied segment of outpatient clients.

Furthermore, the use of structured clinical interviews as part of routine practice as well as the Practice-Research Network (PRN) that has seamlessly been incorporated into the daily operations of the clinic allow the Psychological Clinic to provide both ecologically valid and empirically rigorous data (Castonguay, Locke, & Hayes, 2011). These data will therefore be reliably generalizable to both the research and clinical community, particularly the U.S. community mental health centers.

The StudyFinder which is customized and supported by the Pennsylvania State University Clinical and Translational Science Institute under grant UL1TR000127 is also another excellent resource to tap into. Participants from the community who have been struggling with high levels of social anxiety symptoms and tend to avoid multiple feared social situations experience less social and occupational opportunities in life. This research study offers such community adult participants the chance to break away from such avoidance patterns. To this end, interested participants via StudyFinder who identify with struggling with social anxiety are able receive diagnosis and treatment and thereby improve their quality of life.

16.3 PI Time devoted to conducting the research

Describe how the PI will ensure that a sufficient amount of time will be devoted to conducting and completing the research. Please consider outside responsibilities as well as other on-going research for which the PI is responsible.

This study's PI and project coordinator will devote all necessary research time to completing the study within the next eight semesters (August 2018 to August 2023). The active time burden for study personnel, working with participants before data analysis, does not appear to amount to more than 10

hours per participant, ideally. With 75 participants per semester, the time investment would be 45,000 hours per semester.

16.4 Availability of medical or psychological resources

Describe the availability of medical or psychological resources that participant might need as a result of their participation in the study, if applicable.

If desired, participants recruited from the subject pool may contact the Penn State Psychological Clinic at [contact] or Penn State Counseling and Psychological Services (CAPS) at [contact] for mental health services. Participants may also call the CAN Help phone line at [name] after hours if necessary.

16.5 Process for informing Study Team

Describe the training plans to ensure members of the research team are informed about the protocol and their duties, if applicable.

The current study personnel have already been trained extensively in their duties. If a new individual joins the team, they will undergo a training session of approximately ten hours and—like everyone involved—will be monitored for adequate performance through the study's duration. They will be required to read this IRB protocol for the study, the informed consent, each of the measures, the proposal for the study, and will be given every opportunity to ask questions. They will be walked through the virtual reality exposure therapy assignments, as well as each step of the study. The security measures of the locked room and the computers will be addressed. Last, there will be 0.5 to 1-hour weekly meeting between all study members to address any ongoing issues and track progress.

17.0 Other Approvals

17.1 Other Approvals from External Entities

Describe any approvals that will be obtained prior to commencing the research (e.g., from cooperating institutions, community leaders, schools, external sites, funding agencies).

Not Applicable.

17.2 Internal PSU Committee Approvals

Not Applicable.

Check all that apply:

- Anatomic Pathology – Hershey only – Research involves the collection of tissues or use of pathologic specimens. Upload a copy of HRP-902 - Human Tissue For Research Form on the “Supporting Documents” page in CATS IRB. This form is available in the CATS IRB Library.
- Animal Care and Use – All campuses – Human research involves animals and humans or the use of human tissues in animals
- Biosafety – All campuses – Research involves biohazardous materials (human biological specimens in a PSU research lab, biological toxins, carcinogens, infectious agents, recombinant viruses or DNA or gene therapy).
- Clinical Laboratories – Hershey only – Collection, processing and/or storage of extra tubes of body fluid specimens for research purposes by the Clinical Laboratories; and/or use of body fluids that

had been collected for clinical purposes, but are no longer needed for clinical use. Upload a copy of HRP-901 - Human Body Fluids for Research Form on the “Supporting Documents” page in CATS IRB. This form is available in the CATS IRB Library.

- Clinical Research Center (CRC) Advisory Committee – All campuses – Research involves the use of CRC services in any way.
- Conflict of Interest Review – All campuses – Research has one or more of study team members indicated as having a financial interest.
- Radiation Safety – Hershey only – Research involves research-related radiation procedures. All research involving radiation procedures (standard of care and/or research-related) must upload a copy of HRP-903 - Radiation Review Form on the “Supporting Documents” page in CATS IRB. This form is available in the CATS IRB Library.
- IND/IDE Audit – All campuses – Research in which the PSU researcher holds the IND or IDE or intends to hold the IND or IDE.
- Scientific Review – Hershey only – All investigator-written research studies requiring review by the convened IRB must provide documentation of scientific review with the IRB submission. The scientific review requirement may be fulfilled by one of the following: (1) external peer-review process; (2) department/institute scientific review committee; or (3) scientific review by the Clinical Research Center Advisory committee. NOTE: Review by the Penn State Hershey Cancer Institute Scientific Review Committee is required if the study involves cancer prevention studies or cancer patients, records and/or tissues. For more information about this requirement see the IRB website at: <http://www.pennstatehershey.org/web/irb/home/resources/investigator>

18.0 Multi-Site Research

If this is a multi-site study (i.e., the study will be conducted at other institutions each with its own principal investigator) and you are the lead investigator, describe the processes to ensure communication among sites in the sections below.

18.1 Communication Plans

Describe the plan for regular communication between the overall study director and the other sites to ensure that all sites have the most current version of the protocol, consent document, etc. Describe the process to ensure all modifications have been communicated to sites. Describe the process to ensure that all required approvals have been obtained at each site (including approval by the site’s IRB of record). Describe the process for communication of problems with the research, interim results and closure of the study.

Not Applicable.

18.2 Data Submission and Security Plan

Describe the process and schedule for data submission and provide the data security plan for data collected from other sites. Describe the process to ensure all engaged participating sites will safeguard data as required by local information security policies.

Not Applicable.

18.3 Subject Enrollment

Describe the procedures for coordination of subject enrollment and randomization for the overall project.

Not Applicable.

18.4 Reporting of Adverse Events and New Information

Describe how adverse events and other information will be reported from the clinical sites to the overall study director. Provide the timeframe for this reporting.

Not Applicable.

18.5 Audit and Monitoring Plans

Describe the process to ensure all local site investigators conduct the study appropriately. Describe any on-site auditing and monitoring plans for the study.

Not Applicable.

19.0 Adverse Event Reporting

19.1 Reporting Adverse Reactions and Unanticipated Problems to the Responsible IRB

By submitting this study for review, you agree to the following statement – DO NOT ALTER OR DELETE:

In accordance with applicable policies of The Pennsylvania State University Institutional Review Board (IRB), the investigator will report, to the IRB, any observed or reported harm (adverse event) experienced by a participant or other individual, which in the opinion of the investigator is determined to be (1) unexpected; and (2) probably related to the research procedures. Harms (adverse events) will be submitted to the IRB in accordance with the IRB policies and procedures.

20.0 Study Monitoring, Auditing and Inspecting

20.1 Auditing and Inspecting

By submitting this study for review, you agree to the following statement – DO NOT ALTER OR DELETE:

The investigator will permit study-related monitoring, audits, and inspections by the Penn State quality assurance program office(s), IRB, the sponsor, and government regulatory bodies, of all study related documents (e.g., source documents, regulatory documents, data collection instruments, study data, etc.). The investigator will ensure the capability for inspections of applicable study-related facilities (e.g., pharmacy, diagnostic laboratory, etc.).

21.0 Future Undetermined Research: Data and Specimen Banking

If this study is collecting identifiable data and/or specimens that will be banked for future undetermined research, please describe this process in the sections below. This information should not conflict with information provided in section 9.1.1 regarding whether or not data and/or specimens will be associated with identifiers (directly or indirectly).

21.1 Data and/or specimens being stored

Identify what data and/or specimens will be stored and the data associated with each specimen.

Not applicable.

21.2 Location of storage

Identify the location where the data and/or specimens will be stored.

Not applicable.

21.3 Duration of storage

Identify how long the data and/or specimens will be stored.

Not applicable.

21.4 Access to data and/or specimens

Identify who will have access to the data and/or specimens.

Not applicable.

21.5 Procedures to release data or specimens

Describe the procedures to release the data and/or specimens, including: the process to request a release, approvals required for release, who can obtain data and/or specimens, and the data to be provided with the specimens.

Not applicable.

21.6 Process for returning results

Describe the process for returning results about the use of the data and/or specimens.

Not applicable.

22.4 Test Article(s) (Study Drug(s) and/or Study Device(s))

22.4.1 Description

Provide a brief description of all test articles (drugs (including any foods and dietary supplements), devices and/or biologics used in the research including the purpose of their use and their approval status with the Food and Drug Administration (FDA). Include information about the form of the drug product (e.g., tablets, capsules, liquid).

The VR kit is a technology that has been used in multiple research studies conducting exposure therapy to treat a range of psychiatric disorders. There have been no reports of participants being harmed in any way, shape, or form in the process. Further, VR technology has been around over the past two decades and has been used repeatedly in a wide range of settings. Therefore, it poses no safety concerns.

22.4.2 Treatment Regimen

Describe dose, route of administration and treatment duration. Include information about dose adjustments.

For each participant, the VR kit will be used for 30 minutes per session.

22.4.3 Method for Assigning Subject to Treatment Groups

Describe the randomization process and how the associated treatment assignment will be made.

Using a random number generator with the “RAND” function on Microsoft Excel, the participants will be randomly allocated to either one of the two treatment conditions (General Social Skills training or Job Interview training) or waitlist condition.

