After self-report questionnaires are completed, participants will then complete the baseline clinical interview (paper version of “LIMBIX - Measure - MINI Neuropsychiatric Interview.pdf”) conducted by a study team member who is not the ultimate research therapist. The clinical interview will generally take about 15 to 25 minutes. This interview will be videotaped to conduct reliability assessment on the diagnoses.

Participants who meet the study eligibility criteria will next be contacted by phone by another study team member within a week to receive their random assignment to either the virtual reality exposure therapy condition or the waitlist control condition and to schedule their treatment planning session. Participants in the immediate treatment group will be invited to start treatment soon after the baseline assessments, whereas those in the waitlist control condition will be invited to start this treatment 8 weeks later. The script “LIMBIX - Scripts - Study Therapist to Subject” will be used to facilitate this process.

Within a day the intake assessor completes the initial assessment for an eligible participant, the coordinator will (1) randomly assign the eligible participant who had just completed the interview to their treatment condition, (2) call the participant to inform them of their study condition, and (3) inform their research therapist assigned to be in charge with conducting the 8 to 10 50-minute weekly treatment planning and therapy sessions.

As participants assigned to the treatment condition will begin therapy immediately, the coordinator will communicate this message to the research therapist within a day of the initial assessment.

On the other hand, participants assigned to the waitlist control condition will begin therapy 8 weeks later, and the coordinator will communicate this message within a few weeks after the initial assessment visit.

Once the research therapist receives the message from the coordinator to start scheduling treatment with a particular participant, he or she is expected to contact the participant and set up an appointment within the next one or two weeks depending on their availability.

Step 3: Treatment Planning

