8.2 Sample size determination

If applicable, provide a justification of the sample size outlined in section 8.1 – to include reflections on, or calculations of, the power of the study.

The proposed study is focused on examining the efficacy, acceptability, feasibility, and the experience of the patient when using virtual reality in treating job interview phobia. The number of participants (300 per intervention condition; 300 General Social Skills Training; 300 Job Interview Phobia; 150 Waitlist Control) was based on Kampmann et al. (2016) who conducted a virtual reality study with adults with social phobia and used similar primary outcome measures. In their study, their power calculations estimated that 300 participants/per intervention group would be sufficient to find significant differences (two sided-power, power= 80%, alpha -0.05, G*Power 3.2) based on an effect size of exposure therapy found in a meta-analysis (Powers et al., 2008).

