22.4.5 Blinding of the Test Article

Describe how the test article is blinded.

Not applicable. Study team members and participants will eventually know the assigned condition of each participant.

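### One coordinator makes, sees and passes on each Excel RAND assignment for a known participant, and the plan describes no locked sequence, independent custodian or record of the draw

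*Combined protocol and SAP*

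**What the plan says.** Section 22.4.3 (Method for Assigning Subject to Treatment Groups) names the tool and the arms: the RAND "function on Microsoft Excel, the participants will be randomly allocated to either one of the two treatment conditions", or to waitlist. It does not say who operates the spreadsheet, when, at what ratio, with what blocks or seed, or where the result is kept.

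Section 7.2 (Study Procedures, Step 2) supplies the person and the timing. Within a day of a completed assessment, "the coordinator will (1) randomly assign the eligible participant who had just completed the interview to their treatment condition, (2) call the participant" and then "inform their research therapist assigned to be in charge with conducting the 8 to 10 50-minute weekly treatment planning and therapy sessions".

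The same step contains two further statements that matter here:
- The eligibility interview is "conducted by a study team member who is not the ultimate research therapist", and the intake assessor is described separately from the coordinator.
- A preceding paragraph says that eligible participants are "contacted by phone by another study team member within a week to receive their random assignment". That is a different description of who makes the call and how soon.

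Section 22.4.5 treats blinding as not applicable: "Study team members and participants will eventually know the assigned condition of each participant". This concerns knowledge after assignment and does not address concealment before it.

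Section 8.1 plans 750 participants, and section 8.2 divides them as "300 General Social Skills Training; 300 Job Interview Phobia; 150 Waitlist Control".

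**The concern.** Concealment requires that whoever handles a known participant's assignment can neither foresee nor change it. Here one role covers the draw, the call and the notice to the therapist. Under section 7.2 a VRET assignment needs a therapist straight away, while a waitlist assignment defers treatment by 8 weeks. Tight therapist capacity or an apparently urgent participant could therefore make one result more convenient than the other.

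RAND gives a new value whenever the sheet recalculates. Unless the result is saved as a fixed value, the file will not show which draw was used, and the plan does not ask for it to be saved.

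The comparison at stake is VRET v waitlist, which carries the first hypothesis in section 1.0. Section 8.3 lists only post-treatment and follow-up scores as time points and names no baseline covariate, so the stated analysis would not clearly correct a prognostic imbalance. Even if nothing improper happened, the trial would have no record with which to show it.

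**Working it through.** **Reading the sections together.** The plan states no figure on this point, so there is none to reproduce.

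| Question | Where answered | Answer |
|---|---|---|
| Tool | 22.4.3 | Excel RAND |
| Who assigns | 7.2 | The coordinator |
| When | 7.2 | Within a day of the completed assessment of an eligible participant |
| Is the participant known at that moment? | 7.2 | Yes |
| Who informs participant and therapist | 7.2 | The coordinator (elsewhere in 7.2, another team member calls the participant) |
| Locked list, seed, custodian, release step, log | Nowhere | Not described |

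Two procedures fit this text:
- *RAND is run for each participant.* The coordinator can redraw.
- *A list was made earlier with RAND.* Nothing keeps it from the coordinator, who can see the next entry and override or reorder.

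Section 7.2 reads more like the first. Concealment from the coordinator is missing under both.

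**Illustration of size.** From the plan: N = 750 and 300:300:150, so the pooled ratio of VRET to waitlist is 600:150 = 4:1. Assumed: 10% of participants would do 0.5 SD better, the coordinator recognises them, and all are sent to VRET.

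1. Favoured participants: 0.10 × 750 = 75.
2. Of these, an honest draw would put 0.20 × 75 = 15 on waitlist. These 15 are diverted.
3. Each redraw again gives waitlist with probability 0.20, so the expected number of redraws is 15/0.80 = 18.75, about 19.
4. VRET size: 75 + 0.80 × 675 = 615. Waitlist size: 0.20 × 675 = 135.
5. Bias = 0.5 × (75/615 − 0/135) = 0.061 SD.

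**Benchmark.** The protocol gives no effect size, so the comparison is with the detectable difference at 80% power, two-sided 0.05: (1.960 + 0.842) × √(1/600 + 1/150) = 0.256 SD. Then 0.061/0.256 = 24%. For one VR arm against waitlist (300 v 150) the detectable difference is 0.280 SD, and 0.061/0.280 = 22%.

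**Would arm sizes reveal it?** Under simple 2:2:1 randomisation the SD of the waitlist size is √(750 × 0.2 × 0.8) = 10.95. A fall from 150 to 135 is 15/10.95 = 1.4 SD, which would pass as chance.

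**Sensitivity.**
- Halving the assumed prognostic difference halves the bias, to 0.030 SD.
- With at most one redraw per favoured participant, the chance of waitlist falls from 20% to 0.2 × 0.2 = 4%. Waitlist then holds 3 favoured people of 138 (2.2%) and VRET 72 of 612 (11.8%), a bias of 0.5 × (0.118 − 0.022) = 0.048 SD.
- With a favoured share of 25%, all steered, VRET has 187.5 + 0.80 × 562.5 = 637.5 people and the bias is 0.5 × 187.5/637.5 = 0.147 SD. Waitlist would fall to 112.5, which is 37.5/10.95 = 3.4 SD below plan and would be noticed.

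**The case against.** The strongest reply is that this criticises silence. Section 22.4.3 names no operator and section 7.2 does not mention Excel, so a per-participant RAND draw is obtained only by joining the two. The team may save its draws or work from a list. That stands. A reader might infer that draws are demonstrably repeatable without trace, but the documents say only that no record is described. What survives is that neither possible procedure conceals the assignment from the coordinator.

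Second, there is real separation at entry. Consent, questionnaires and interview precede assignment, and the interviewer is not the eventual therapist. A reader might infer that allocation is open to whoever enrols participants. The documents do not support that: if the draw follows eligibility, the assessor has no future assignment to foresee. The risk narrows to the coordinator.

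Third, the motive is uncertain. Nothing says that the coordinator sees baseline data or meets participants before assigning them, and waitlisted participants are offered treatment 8 weeks later. Both points make steering less likely. Neither gives the trial a means of showing that it did not happen.

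Fourth, a reader might set the bias against the 0.229 SD detectable with 300 v 300 and get 27%. That benchmark compares one VR module with the other and is not an effect that the plan states. For pooled VRET v waitlist the figure is 24%.

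**Conclusion.** The point holds as a weakness in the described procedure. The plan names a method in which the person who makes the assignment also implements it, for a known participant, and it describes no safeguard or record. It is not evidence that any assignment was or will be manipulated.

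The size is illustrative: about 0.06 SD, or about 24% of the detectable difference for 600 v 150. It rests on a 10% share, a 0.5 SD advantage, complete steering and a 4:1 ratio, none of which except the ratio comes from the plan. The bias rises and falls with the assumed share and prognostic difference. The useful message is that about 15 diverted participants, 15/750 = 2% of assignments, are enough, and that arm sizes would not show it.

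A reader might also take VRET v waitlist to be the only randomised comparison. Section 22.4.3 randomises to three conditions, so the two VR modules are randomised there too, whereas section 7.2 describes two arms with the module settled after assignment. That conflict is a separate matter, but it must be resolved before an allocation ratio can be written down.

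**What to change.** Amend sections 22.4.3 and 7.2 as follows.

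1. Reconcile the two-arm wording in 7.2 with the three-arm wording in 8.2 and 22.4.3, and state the allocation ratio.
2. Replace the coordinator's RAND draw with a sequence generated once before enrolment, stored as fixed values with the seed archived. Use randomly varied block sizes that are not disclosed to recruiting staff. In a single-site, unblinded trial, known fixed blocks would let late assignments in a block be predicted.
3. Have the sequence held by an existing team member with no participant contact, or in a locked electronic randomiser.
4. Release one assignment at a time, time-stamped, only after eligibility has been recorded, and keep the release log.
5. Reconcile who tells the participant and when: the coordinator within a day, or another team member within a week.

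The cost is a small amount of set-up work and a short release step for each participant. The change cannot repair assignments already made, so it should be in place before any further participant is assigned.
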